#### **CGM Monitoring of Usual Care Days 1–6 (5 days):**

- An additional calibration will be performed by the study staff before breakfast and before study start at 3:00 PM using the HemoCue meter.
- A member of the study staff will be monitoring all volunteers in the usual care arm via telemetry around the clock. The staff monitoring telemetry will be able to communicate with camp healthcare providers by radio or cell phone and there will be a study “runner” on call to deal with any issues that may arise with functioning of study device or if telemetry staff is unable to contact the cabin camp healthcare provider.
- The G4 CGM system will be blinded to the volunteers and the high and low glucose alarms will be turned off. This will ensure that volunteers will not use this data to modify their BG control strategy. The screen of the bionic pancreas control unit will be locked except for access to enter BG values and all audible alarms will be silenced. The bionic pancreas worn by volunteers in the usual care arm will be streaming data to the SweetSpot cloud service for remote real-time monitoring by study staff, but it will not be controlling insulin or glucagon infusion.
- All BG values taken as a part of usual care will be entered into the bionic pancreas interface.
- The experimental period will begin at 3:00 PM on the first day of the camp session (Sunday).
- Over the next five days (3:00 PM Sunday to 3:00 PM Friday) volunteers will have their BG managed according to the camp’s health care manual. All BG measurements will be performed by study staff or camp healthcare providers with the HemoCue device. Study staff will calibrate the G4 before breakfast and before supper with the HemoCue BG meter.
- During the experiment the bionic pancreas device will be worn by the volunteer or kept nearby (such as when sleeping) at all times to ensure good radio-frequency signal reception. The device may be removed for short periods of time (no more than 30 minutes) for showering and swimming.
- If during the course of an experiment, a DexCom G4 sensor fails (reports sensor failure, ceases

to transmit data, reports multiple calibration failures, or reports questionable data) a new sensor will be inserted and calibrated.

- Volunteers who are counselors will have to remain on the camp grounds during their days off.
- There will be a camp health care provider assigned to each camp cabin throughout the usual care period.

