- Camp nurses will be asked to document all hypoglycemia and carbohydrate interventions for hypoglycemia.
- Camp nurses and counselors will be asked to maintain a schedule of active and less active sessions for each camper.
- As a difference from the camp usual care protocol, BG levels will be measured at midnight and 3:45 AM (regardless of the value at 12:00 AM) using the HemoCue point of care BG meter. There may be additional BG checks between 11 pm and 7 am as determined by a nocturnal hypoglycemia alert system (see closed-loop section below). Extra BG checks may be performed during the day depending on how many episodes of hypoglycemia occur (which trigger more frequent measurements), or on order of the resident camp physician.
- The only other difference from usual camp protocol is that hypoglycemia intervention rules will follow the same protocol as in the closed-loop BG control group (described below).
- At 3:00 PM on day 6 (Friday) the usual care portion of the experiment will end. The DexCom CGM will be removed.
- The volunteer's insulin pump will be downloaded for information on insulin dosing and carbohydrate intake during the usual care period.

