- There is no area of the camp that is commonly visited by campers that is more than ~ 300 yards from any other area, so it will be easy for study staff to circulate and to get from one area to another if needed. Under the unusual circumstances when campers go further than this (i.e. for a hike) a study staff member will accompany that group carrying all needed supplies (which will also be duplicated by the camp RN/NG who will also accompany such groups. The remaining members of the study team will remain at the main camp area, maintaining the same ratio of study staff to subjects.
- Before disconnecting from the device for shower:
 

BG	Treatment
< 100 mg/dl	15g rapid acting carbohydrate
- Over the next five days (3:00 PM Sunday to 3:00 PM Friday) the bionic pancreas will control insulin and glucagon dosing and the volunteers will otherwise be treated according to camp guidelines except for specifically noted exceptions in the protocol.
- During closed-loop control the glucose measurements from the CGM will be transmitted to the bionic pancreas. The control algorithm will respond by commanding SC doses of insulin and/or glucagon as appropriate through the Tandem t:slim pumps.
- During the experiment the bionic pancreas device will be worn by the volunteer or kept nearby (such as when sleeping) at all times to ensure good radio-frequency signal reception. The device may be removed for short periods of time (no more than 30 minutes) for showering and swimming.
- If during the course of an experiment, a DexCom G4 sensor fails (reports sensor failure, ceases to transmit data, reports multiple calibration failures, or reports questionable data), the bionic

pancreas will automatically switch to giving basal insulin based on historical basal insulin needs at that time of the day. In addition, any BG measurements entered into the bionic pancreas will be used to dose insulin and glucagon as if they were CGM values and the system will continue to accept meal announcements. A new sensor will be inserted and closed-loop control will automatically resume once the new sensor is initially calibrated.

- Meals will be announced to the control algorithm 15-20 minutes prior to the meal at the same time as meal boluses are delivered for other campers. Low BG will be treated as usual, except that no action will be taken for  $BG > 70$  mg/dl.

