#### **V. e. Response to Hypoglycemia**

- All subjective symptoms of hypoglycemia will be investigated with a capillary BG using a HemoCue meter.
- Volunteers in both of the study arms (closed-loop and usual care) will take carbohydrates to treat hypoglycemia or symptoms consistent with hypoglycemia according to a protocol modified from the usual camp protocol as follows:
- Mild hypoglycemia (mild signs and symptoms or BG 60–80 mg/dl, able to self treat):
  - Wait 15–20 minutes and recheck BG
  - If BG is still < 70 give 15 gm of rapid-acting carbohydrates (glucose tabs, juice, milk, gel, etc.)
- The modified hypoglycemia protocol is intended to allow auto-treatment of mild hypoglycemia with glucagon by the control algorithm to occur without being preempted by carbohydrates given prior to the onset of hypoglycemia (for instance in the 70-80 mg/dl range) or when hypoglycemia is mild (BG 60-70 mg/dl). In order to maintain safety, a second BG check in 15-20 minutes is included so that hypoglycemia is treated if not averted by the closed-loop system.
- For experimental validity, the same modifications from camp policy need to be used for both the closed-loop and open-loop arms of the study. Note that treatment of BG < 60 mg/dl will be according to the normal camp protocol in both arms (immediate treatment with rapid-acting carbohydrates) AND subjects may take carbohydrates at any time for symptoms when BG is < 80 mg/dl
- Camp healthcare providers and camp counselors will carry rapid acting and complex carbohydrate interventions with them at all times. All carbohydrate treatments for hypoglycemia will be documented by study staff (amount and time).
- In any case in which two rapid-acting carbohydrate interventions must be administered by camp protocol or if glucagon is administered manually by injection, a study staff member will check the operation of the bionic pancreas system. Consideration will be given to replacing the glucagon infusion set and/or recalibrating the CGM.

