### **Secondary endpoint analyses – Non-glycemic:**

- All of following metrics will be generated from the closed-loop and usual care periods and the differences will be reported unless otherwise specified:
- Number of carbohydrate interventions for hypoglycemia (day and night)
- Total number of grams of carbohydrate taken for hypoglycemia (day and night)
- Insulin total daily dose
- Mean daily basal insulin dose
- Mean daily bolus insulin dose
- Number of carbohydrate interventions for hypoglycemia during the daytime (7:00 AM – 11:00 PM)
- Total number of grams of carbohydrate taken for hypoglycemia during the daytime ((7:00 AM – 11:00 PM)
- Number of carbohydrate interventions for hypoglycemia overnight (11:00 PM – 7:00 AM)
- Total number of grams of carbohydrate taken for hypoglycemia overnight (11:00 AM – 7:00 AM)
- Mean meal carbohydrate content
- The following metrics will be generated from the closed-loop period:
- Insulin lispro dosing (u/kg/24 hours)
- Glucagon dosing (mcg/kg/24 hours)
- Fraction of time bionic pancreas in open-loop mode due to loss of CGM signal
- Fraction of time bionic pancreas completely off-line
- Fraction of time bionic pancreas off-line or not functioning properly for each of the following reasons: system crash, communication problem between CGM and bionic pancreas, communication problem between bionic pancreas and pumps, pump malfunction, tubing occlusion, infusion set failure/pulled out
- Difference in mean insulin dose per hour during periods of normal operation vs. periods of bionic pancreas downtime
- Fraction of bionic pancreas downtime during which automatic basal rate suspended or reduced
- Difference in mean insulin dosing during the four hour period after a meal during periods of normal operation vs. periods of bionic pancreas downtime (open-loop dosing)
- Difference of outcome measures on day 1 vs. remaining days (days 2-5) and on day 1-2 vs. on remaining days (days 3-5)
- All of following metrics will be generated from the closed-loop, usual care periods, and from the non-participants and the differences will be reported unless otherwise specified:
- Number of carbohydrate interventions for hypoglycemia (day and night)
- Total number of grams of carbohydrate taken for hypoglycemia (day and night)
- Insulin total daily dose
- Mean daily basal insulin dose
- Mean daily bolus insulin dose
- Number of carbohydrate interventions for hypoglycemia during the daytime (7:00 AM – 11:00 PM)

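### The pre-shower carbohydrate rule appears only in the closed-loop section, is not reconciled with the hypoglycemia rules, and some of its grams escape the carbohydrate-intervention endpoints

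*Combined protocol and SAP*

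**What the plan says.** **The rule.** Section V. d. iii, under Closed-loop Blood Glucose Control Days 1–6, has an item headed "Before disconnecting from the device for shower". It assigns "15g rapid acting carbohydrate" when BG is below 100 mg/dl and gives no lower limit.

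**Usual care.** The section on CGM Monitoring of Usual Care Days 1–6 also allows disconnection: "The device may be removed for short periods of time (no more than 30 minutes) for showering and swimming". It attaches no carbohydrate rule. After listing the extra overnight BG checks, it states: "The only other difference from usual camp protocol is that hypoglycemia intervention rules will follow the same protocol as in the closed-loop BG control group". The camp-policy summary in V. d. ii has no shower rule. The full manual is Appendix D.

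**Hypoglycemia response.** Section V. e modifies camp policy for both arms. At BG 60–80 mg/dl, or with mild symptoms, staff wait 15–20 minutes, recheck, and give 15 g only if BG is still below 70. The stated purpose is to let automatic glucagon act before carbohydrate does, including at 70–80 mg/dl. BG below 60 is treated at once, and volunteers may take carbohydrate for symptoms at any time when BG is below 80. It adds: "For experimental validity, the same modifications from camp policy need to be used for both the closed-loop and open-loop arms of the study".

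**Meals in closed loop.** The meal-announcement item says low BG is treated as usual, but with no action above 70 mg/dl.

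**Endpoints.** The non-glycemic secondary endpoints in VI. b count the number and the grams of carbohydrate taken *for hypoglycemia*. V. e requires staff to document amount and time for hypoglycemia treatments. Estimated carbohydrate intake is collected in both periods (VI. a).

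**The concern.** Aim 1 names hypoglycemia requiring carbohydrate as a secondary outcome, so the count and grams of such treatments will be read as evidence on how much rescue each strategy needs. A rule that gives carbohydrate in the visible text of one arm only, partly at BG levels the protocol does not call hypoglycemia, can make that arm look less dependent on carbohydrate than it was. If the rule exists because disconnecting interrupts the device, the carbohydrate is part of the closed-loop strategy and belongs in its account.

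The instructions also collide. A staff member who reads 75 mg/dl before a shower is told by one section to give carbohydrate now and by another to wait and recheck. What is done may then vary between staff, and so may what is recorded as a hypoglycemia treatment.

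**Working it through.** The plan states no figure on this point, so there is nothing to reproduce. The check sets the instructions side by side by BG level and then sizes the possible undercount.

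**Side by side, closed-loop volunteer about to shower**

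- *Below 60 mg/dl.* V. e: immediate rapid-acting carbohydrate. Shower rule: 15 g. Both give carbohydrate, and it should count as treatment for hypoglycemia.
- *60–69 mg/dl.* V. e: wait and recheck, unless the volunteer takes carbohydrate for symptoms. Shower rule: 15 g now. The instructions conflict. The grams could be counted, but the plan does not say so.
- *70–80 mg/dl.* V. e: wait and recheck, with carbohydrate only if BG is then below 70. Meal item: no action above 70, though its scope may be meals only. Shower rule: 15 g now. The instructions conflict. V. e labels this band mild hypoglycemia, while the BG endpoints use 70 mg/dl as the cut-off, so classification is unclear.
- *80–99 mg/dl, no symptoms* (80 itself is the edge of the mild band). Shower rule: 15 g. Above the edge, no protocol definition calls this hypoglycemia, so the grams enter neither endpoint. The other carbohydrate endpoint, mean meal content, does not capture them either.

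**Size of the possible undercount**

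From the documents: 15 g per trigger; 5 days of closed loop; 32 expected completers (IV. a). Assumed, because the documents give neither: s showers per day, and p, the share of showers with BG below 100. Let q be the share of triggered treatments that go uncounted; q is also unknown.

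- Uncounted treatments per volunteer = 5 × s × p × q; uncounted grams = 15 × that number.
- With s = 1, p = 10–30% and q = 1 (the ceiling): 5 × 0.10 = 0.5 to 5 × 0.30 = 1.5 treatments, or 7.5 to 22.5 g per volunteer. Over 32 volunteers this is 16 to 48 treatments.
- Outer range, s = 1–2 and p = 10–100%, q = 1: 15 × 5 × 1 × 0.10 = 7.5 g to 15 × 5 × 2 × 1 = 150 g per volunteer, or 240 to 4,800 g over 32.
- Any q below 1 scales these down in proportion.

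**Co-primary percentage below 70 mg/dl**

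Section V. c sets at least seven HemoCue checks per day in closed loop; one secondary analysis in VI. b uses six. One averted scheduled reading below 70 moves a volunteer's percentage by 100/(7 × 5) = 2.9 points, or 100/(6 × 5) = 3.3 points. This shows the weight of one reading and does not estimate an effect: nothing in the documents links shower times to scheduled checks, so the number of averted readings is unknown.

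**The case against.** **Breach of the equal-rules principle.** A reader might infer that the shower rule plainly violates V. e. The text does not go that far. The sentence sits in the section on response to hypoglycemia and refers to the wait-and-recheck change described there. There is also a dilemma: if the rule is a hypoglycemia intervention, the usual-care section may already import it and its grams may be counted; if it is preventive, it lies outside the principle. This limits the point to a failure to reconcile. It does not remove it, because the plan never says which reading applies.

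**The arms differ at disconnection.** In usual care the study unit does not control insulin or glucagon, so removing it withdraws no treatment. In closed loop, disconnection interrupts dosing. A rule in one arm may be deliberate, and Appendix D may cover usual-care pumps. Both points stand. They are reasons to state the scope, and they do not settle how the grams are counted.

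**Only closed loop gets uncounted preventive carbohydrate.** A reader might infer this, but the documents contradict it. The camp summary gives activity snacks (30–40 g for hiking, 15–20 g for adventure activities), and bedtime snacks without insulin coverage at BG 70–99. These are not counted as hypoglycemia treatment either.

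**All pre-shower grams are lost.** This is too broad. The rule has no lower limit, so some grams fall where they could be counted, and general carbohydrate intake is collected in both arms.

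**The co-primary is biased in favour of the device.** This is not shown. Scheduled readings are not tied to showers, and extra carbohydrate would tend to raise closed-loop mean BG, the other co-primary, which works against the device.

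**Conclusion.** The point holds in limited form. On the text supplied, the pre-shower rule is in the closed-loop section only and is not reconciled with the wait-and-recheck step, the equal-modifications statement, the shared intervention rules, or the no-action wording in the meal item. As worded, asymptomatic grams given at 80–99 mg/dl are outside both hypoglycemia-carbohydrate endpoints, and the status of grams given below 80 is unclear. The comparison of carbohydrate interventions can therefore understate closed-loop use.

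The size is probably modest: at most 0.5–1.5 treatments per volunteer over five days under one daily shower and 10–30% of showers below 100 mg/dl, neither of which the documents supply. An effect on the co-primary percentage below 70, or on the closed-loop criterion of less than 5% below 70 in VI. d, is possible but unquantified. The arm difference is conditional on Appendix D holding no camp-wide rule. The point merits correction because the remedy is cheap; it does not by itself threaten the primary comparison.

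**What to change.** 1. Reconcile the shower item in V. d. iii with the meal item there, with the usual-care section and with V. e, and state whether the rule applies in both arms. The clinical team decides the rule. If Appendix D already covers it, cite it.
2. Record the amount, time and BG of every carbohydrate given before a disconnection, in both arms, and state in advance how grams given below 80 mg/dl are classified.
3. Keep the hypoglycemia-treatment endpoints as defined. Alongside them, report the number and grams with pre-disconnection carbohydrate included. Adding these grams to the endpoint itself would mix prevention with treatment while other preventive carbohydrate stays out.

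The cost is one line on the documentation form and one extra summary. The closed-loop carbohydrate total may look slightly less favourable in the added version.

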#### **Transition Between Study Arms:**

- After the first arm of the study is completed on Friday at 3:00 PM, volunteers will go back to usual care camp protocols until Saturday afternoon, when a new DexCom G4 CGM sensor will be placed.
- Volunteers who were randomized to the closed-loop arm will switch to the usual care arm in the second week, and vice versa.

#### **V. e. Response to Hypoglycemia**

- All subjective symptoms of hypoglycemia will be investigated with a capillary BG using a HemoCue meter.
- Volunteers in both of the study arms (closed-loop and usual care) will take carbohydrates to treat hypoglycemia or symptoms consistent with hypoglycemia according to a protocol modified from the usual camp protocol as follows:
- Mild hypoglycemia (mild signs and symptoms or BG 60–80 mg/dl, able to self treat):
  - Wait 15–20 minutes and recheck BG
  - If BG is still < 70 give 15 gm of rapid-acting carbohydrates (glucose tabs, juice, milk, gel, etc.)
- The modified hypoglycemia protocol is intended to allow auto-treatment of mild hypoglycemia with glucagon by the control algorithm to occur without being preempted by carbohydrates given prior to the onset of hypoglycemia (for instance in the 70-80 mg/dl range) or when hypoglycemia is mild (BG 60-70 mg/dl). In order to maintain safety, a second BG check in 15-20 minutes is included so that hypoglycemia is treated if not averted by the closed-loop system.
- For experimental validity, the same modifications from camp policy need to be used for both the closed-loop and open-loop arms of the study. Note that treatment of BG < 60 mg/dl will be according to the normal camp protocol in both arms (immediate treatment with rapid-acting carbohydrates) AND subjects may take carbohydrates at any time for symptoms when BG is < 80 mg/dl
- Camp healthcare providers and camp counselors will carry rapid acting and complex carbohydrate interventions with them at all times. All carbohydrate treatments for hypoglycemia will be documented by study staff (amount and time).
- In any case in which two rapid-acting carbohydrate interventions must be administered by camp protocol or if glucagon is administered manually by injection, a study staff member will check the operation of the bionic pancreas system. Consideration will be given to replacing the glucagon infusion set and/or recalibrating the CGM.

#### **V. f. Response to Hyperglycemia**

- Any time a ketone check is mandated by camp protocol the closed-loop system will be checked for any malfunction and any such problems will be corrected. The insulin infusion set will be replaced if mandated by camp protocol or if there is any doubt as to its proper functioning.
- If no correctable fault is found, but there is doubt regarding the correct function of the bionic pancreas system, an entirely new backup bionic pancreas system may be started.
- While the new system is being replaced and calibrated the volunteer will use their own pump in open loop mode according to usual care camp protocols.
- If the blood ketone result is  $\geq 0.6$ mmol/dL a study physician or nurse practitioner will be notified and will evaluate the volunteer in person.

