**Ketone monitoring:**

Blood or urine ketones are checked when BG readings are > 250 or with complaints of illness. Blood ketone results are preferred when a camper is on Depokote, and cases of suspected diabetes ketoacidosis.

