**Hyperglycemia management, BG is  $\geq$ 250 mg/dl:**

- Check ketones (urine or blood)
- Negative ketones (trace urine ketones, < 0.6 mmol/l blood ketones)
  - Give a correction to the ordered target (typically 120–150) and increase fluids

- May continue activity
- Recheck in 1 hour If the blood sugar is coming down, recheck in another hour until BG < 250 mg/dl.
- If the blood sugar is going up, give the correction by injection and change the pump site
- Positive ketones (small urine ketones or  $\geq 0.6$  mmol/l blood)
  - Change the pump site and increase fluids.
  - Give insulin correction by injection to ordered target (typically 120–150 mg/dl).
  - Obtain hourly blood glucose readings.
  - Discontinue activity until ketones have cleared
  - Notify the physician of blood sugar reading >300 mg/dl and anytime there are positive ketones.

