**V. d. iii. Study-specific Procedures**

**Closed-loop and Usual Care Visit Day 0 – DexCom G4 Platinum Sensor Placement:**

- Volunteers will check in to the camp the day before the start (Saturday) at 11:00AM.
- Up to 8 volunteers may perform a closed-loop experiment at the same time and be integrated with the other campers’ accommodations. During bedtime hours study staff will have the ability to access all cabins so that they can respond to any issues or emergencies that may arise.
- Volunteers will bring any routinely used medications. The camp will be responsible for dispensing medications other than insulin and glucagon during the closed-loop portion of the experiment. During usual care, all medications will be dispensed by the camp.

- Any medical advice needed by the volunteers during their participation that is not directly related to BG control during the experiment should be obtained by them in the usual manner at camp.
- Subjects may take any over-the-counter medications that are recommended by the camp physician during the trial except acetaminophen, which will not be allowed due to potential interference with CGM sensing.
- If a volunteer develop an illness during the experiment camp guidelines will be used for sick day management. If vomiting occurs, a study physician or nurse practitioner will be notified and will evaluate the volunteer in person.
- Female volunteers post-menarche will provide a urine sample for urine pregnancy testing. If the test is positive the volunteer (and legal guardian if less than 18 years of age) will be informed of the result by the study staff and they will be excluded from participating.
- Height, weight, blood pressure and temperature will be measured. A brief history and physical will be performed by a study physician or nurse practitioner.
- The DexCom G4 sensor will be placed by 1:00 PM and linked to the CGM receiver in the bionic pancreas control unit. For volunteers in the control arm the bionic pancreas control unit will have a modified interface that does not report CGM glucose, but does include an interface to allow entry of BG values.
- Initial calibration (at 2 hours after placement, at approximately 3:00 PM) will be performed by the study staff using the HemoCue meter.
- An additional calibration will be performed before dinner.
- Volunteers have their BG managed according to usual camp protocols until the following day.

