#### **V. i. Supervision by Study Staff**

A study physician or nurse practitioner will be available at the camp at all times during the course of each experiment. Trained study staff will also be continuously monitoring the function of each bionic pancreas via remote telemetry 24 hours a day throughout the experiment from a central location in the camp. The clinicians will also have the capability of remotely viewing the controller display on their iPhone or iPad and evaluating diagnostic information during the experiment to facilitate clear communication with nurses.

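### The rule requiring a study clinician to see a volunteer with ketosis is triggered only by a blood ketone result, although the check behind it may be done on urine

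*Combined protocol and SAP*

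**What the plan says.** Three sets of rules in the combined protocol and SAP meet here.

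- **The check itself** comes from the camp rules summarised in V.d.ii. Under Ketone monitoring: "Blood or urine ketones are checked when BG readings are > 250 or with complaints of illness". Hyperglycemia management likewise allows either specimen.
- **What counts as positive** is also a camp rule: "Positive ketones (small urine ketones or" a blood value of at least 0.6 mmol/l). A positive result by either route leads to a pump site change, insulin correction by injection, hourly glucose readings, a stop to activity, and this escalation: "Notify the physician of blood sugar reading >300 mg/dl and anytime there are positive ketones".
- **The study's additional steps** are in V.f. One applies whatever the specimen: "Any time a ketone check is mandated by camp protocol the closed-loop system will be checked for any malfunction". The other, the last bullet of V.f, does not. It begins "If the blood ketone result is" (at or above 0.6), and the action is that "a study physician or nurse practitioner will be notified and will evaluate the volunteer in person".

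**The concern.** The protocol added evaluation by a study clinician on top of camp care. As worded, two volunteers who are both ketone-positive by the camp's definition are treated differently on that step only because of the specimen tested. Nothing in the text suggests this was intended, since the camp rules give urine its own positive threshold.

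The step is not a mere duplicate of camp physician notification. Section V.d.iii says camp healthcare providers receive only basic training on the closed-loop system. The camp response to positive ketones includes insulin by injection, whereas Section I.c explains that insulin given through the controller is tracked to avoid stacking. It is an inference, but a reasonable one, that insulin given outside the controller is a situation where a clinician who knows the device adds something.

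**Working it through.** No calculation in the plan bears on this, so the check sets the rules side by side.

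**Step 1: does any rule force a blood test?**

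- Ketone monitoring (V.d.ii) prefers blood in two situations, a named medication and suspected ketoacidosis. That is a preference, not a requirement.
- In the closed-loop period, V.d.iii applies camp guidelines except where the protocol notes an exception. No noted exception concerns the ketone specimen.
- In the usual care period, the stated departures from camp care concern overnight glucose checks and hypoglycemia treatment, not ketones.
- No supplied text asks for blood confirmation after a positive urine result.

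**Step 2: what does each volunteer receive?** Applying the rules literally during closed loop:

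| Result | Device check (V.f) | Camp treatment and physician notified (V.d.ii) | In-person study evaluation required |
|---|---|---|---|
| Blood at or above 0.6 | Yes | Yes | Yes (V.f) |
| Urine positive, then blood at or above 0.6 | Yes | Yes | Yes (V.f) |
| Urine positive, no blood test, vomiting | Yes | Yes | Yes (vomiting rule, V.d.iii) |
| Urine positive, no blood test, not vomiting | Yes | Yes | **No** |

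The vomiting rule in the third row reads "If vomiting occurs, a study physician or nurse practitioner will be notified and will evaluate the volunteer in person". It does not depend on ketones. The gap is the fourth row, and only in its last column.

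**Step 3: would the result reach a study clinician by another stated route?** The data that IX.a describes as streamed to the monitoring station are CGM, calibration, insulin and glucagon dosing, and HemoCue values. Ketone results are not in the data lists of VI.a for either period. A study clinician may well hear of a positive urine result, but no supplied rule requires it.

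**Step 4: size.** The camp definition has two routes to a positive result, and the V.f trigger names one of them. Closed-loop exposure is 32 volunteers × 5 days = 160 volunteer-days. The last bullet of V.f names no arm; if it also covers usual care, exposure is 32 × (5 + 5) = 320 volunteer-days. These are days on which the rule could apply, not days affected by the gap. The rate of ketone checks and the share done on urine are not given.

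**The case against.** The strongest objection is that the camp rules in the protocol are a summary. The full manual is Appendix D, which was not available for this review. If it makes blood testing the norm, or requires blood after a positive urine test, the fourth row of the table is empty in practice. This stands as a limit on the finding. It would still leave V.f not saying so.

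Second, the uncovered group is probably the milder one. Suspected ketoacidosis steers staff towards blood, and vomiting brings an evaluation anyway. This is fair, though a preference for blood does not guarantee a blood test.

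Third, study staff are close by. Telemetry is watched around the clock, and by day study nurses and clinicians circulate with attention to volunteers at higher risk of high or low glucose (V.d.iii). V.i adds: "A study physician or nurse practitioner will be available at the camp at all times during the course of each experiment". A volunteer whose glucose prompts a ketone check is one this system is meant to notice, so an informal evaluation is plausible. Availability is still not the same as the required evaluation that V.f gives to a blood-positive volunteer.

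Finally, no effect on the co-primary endpoints, the analysis or the success criteria is shown. That is correct, and none is claimed.

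**Conclusion.** The concern holds at its stated scope. Followed exactly, V.f does not require a study physician or nurse practitioner to see a volunteer who is urine-positive, not vomiting and without a blood test. Severity is minor: no untreated ketosis follows from the wording, because treatment, device check and camp physician notification apply to either specimen. The number of volunteers affected cannot be estimated from the documents. The conclusion assumes that Appendix D does not already require blood testing or blood confirmation. It does not rest on the exposure figures, nor on the unit printed in V.f (mmol/dL, against mmol/l in the camp rules), which is a separate matter.

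**What to change.** Replace the last bullet of V.f with: *If ketones are positive by the camp definition (small or greater urine ketones, or blood ketones at or above 0.6 mmol/l), a study physician or nurse practitioner will be notified and will evaluate the volunteer in person.* The sponsor's clinicians should confirm the threshold.

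This is a one-sentence change with no new tests or staff. The cost is a few more in-person evaluations by a clinician already at camp.

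An alternative is to require a blood ketone test after any positive urine result. That keeps a quantitative trigger but adds a test. If Appendix D already requires it, a statement to that effect in V.f would be enough.
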